Study Document Cover Page

Official Title: : The Effects of Cardiovascular Autonomic Neuropathy (CAN) on Acute Kidney Injury and Outcome Parameters in Patients Undergoing Isolated Coronary Artery Bypass Grafting (CABG)

NCT Number:

NCT ID not yet assigned

Document Type:

Study Protocol with Statistical Analysis Plan and Informed Consent Form

Document Date:

October 1, 2020

Sponsor / Institution:

Akdeniz University Faculty of Medicine, Department of Anesthesiology and Reanimation

Principal Investigator:

[name]

Contact Information:

[contact]

Study Protocol

Title: The Effects of Cardiovascular Autonomic Neuropathy (CAN) on Acute Kidney Injury and Outcome Parameters in Patients Undergoing Isolated Coronary Artery Bypass Grafting (CABG)

Document Date: October 1, 2020

Institution: Akdeniz University Faculty of Medicine, Department of Anesthesiology and Reanimation

Principal Investigator: [name]

1. Study Objective

This study aims to analyze the effects of cardiovascular autonomic neuropathy (CAN) on primary outcome of acute kidney injury (AKI) and secondary outcome parameters in patients undergoing coronary artery bypass grafting (CABG) with extracorporeal circulation (ECC).

Specifically, the study will investigate:

The incidence of CAN in patients scheduled for isolated CABG

The effect of CAN on AKI

The impact of CAN on outcome parameters (mortality and morbidity)

The relationship between changes in regional cerebral oxygen saturation (rSO_2) and CAN

CAN Diagnosis:

1. Valsalva maneuver
2. Sitting-to-standing test
3. Temperature sensitivity test

2. Materials and Methods

This is a prospective multicenter study including all patients scheduled for CABG requiring ECC.

Preoperative CAN diagnosis will be performed 1 day before surgery using Valsalva maneuver, sitting-to-standing test, and temperature sensitivity test. A positive result in at least two tests will confirm CAN.

Preoperative data to be recorded:

Demographics and comorbidities (hypertension, diabetes, COPD, recent MI, atrial fibrillation, dyslipidemia)

Kidney function (BUN, creatinine, GFR)

Hemodynamic parameters before anesthesia induction

Baseline rSO_2 (monitoring will be blinded for clinical purposes)

Intraoperative data:

Hemodynamics, urine output, blood gases

Total cardiopulmonary bypass time, aortic cross-clamp time

Number of coronary artery anastomoses

Postoperative data:

rSO₂ at 1st and 4th hours, and 60 minutes after extubation

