Intubation duration, prolonged mechanical ventilation, inotropic agent use

Renal function (BUN, creatinine, GFR) and urine output at 24, 48 hours, and 7th day per KDIGO criteria

Postoperative complications (reoperation, mediastinitis, perioperative MI, neurological complications)

Transfusion volume, IABP use, drainage volume

ICU and hospital length of stay, mortality

3. Acute Kidney Injury (KDIGO Criteria)

Stage	Serum Creatinine	Urine Output
1	1.5–1.9× baseline or >0.3 mg/dL increase	<0.5 mL/kg/hr for 6 hrs
2	2.0–2.9× baseline	<0.5 mL/kg/hr for 2 consecutive 6-hr periods
3	≥3× baseline or >4 mg/dL or RRT initiation	<0.3 mL/kg/hr for ≥24 hrs or anuria ≥12 hrs

4. Intraoperative Management

IV crystalloid infusion ≥100 mL/h from anesthesia induction

Mean arterial pressure maintained between 60–100 mmHg

If MAP <60 mmHg → 5 mg ephedrine

Inotropic agents per standard clinical practice

Transfusion if Hct <27%

Hourly urine output monitoring

ECC pump flow >1.8 L/m²/min

Body temperature during ECC ≥28°C

6. Outcomes

Intubation duration
Prolonged mechanical ventilation
Inotropic agent use
Renal failure (KDIGO criteria)
Neurological injury (stroke, confusion, agitation, memory loss, seizure, neurocognitive dysfunction)
Reoperation
Mediastinitis
Transfusion requirement
IABP use
Postoperative drainage
Perioperative MI
ICU and hospital length of stay
Mortality

7. Inclusion and Exclusion Criteria

Inclusion:

All patients >18 years old scheduled for CABG requiring ECC

Exclusion:

Emergency or revision surgeries

Orthopedic issues preventing standing test

Chronic respiratory diseases (bronchitis, asthma, COPD) affecting Valsalva reliability

Uncontrolled hypertension

Use of antiarrhythmic drugs affecting heart rate-based tests

Chronic kidney failure

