Statistical Analysis Categorical variables will be presented as counts and percentages. Between-group comparisons for categorical variables will be performed using the chi-square test. The distribution of continuous variables will be evaluated using skewness and kurtosis. Variables with distribution between -1.5 and +1.5 will be considered normally distributed (parametric), otherwise non-parametric. Parametric continuous variables will be expressed as mean \pm SD. Between-group comparisons will be performed using the independent Student's t-test, and within-group temporal comparisons using the paired Student's t-test. Non-parametric continuous variables will be presented as median and interquartile range (IQR). Between-group comparisons for non-parametric variables will be performed using the Mann-Whitney U test, and within-group temporal comparisons using the Wilcoxon signed-rank test. Correlation analysis will be conducted using Pearson (parametric) or Spearman (non-parametric) correlation coefficients. Factors affecting AKI and neurological complications will be evaluated using multiple regression analysis.

Sample Size Calculation The primary objective of this study is to compare the incidence of AKI between CAN-positive and CAN-negative patients undergoing coronary artery bypass grafting (CABG). Based on previous studies using heart rate variability (HRV) for CAN diagnosis, the prevalence of CAN after myocardial infarction (MI) is approximately 60%. In the CABG population, approximately 30% of patients have diabetes and/or MI. Therefore, we anticipate a CAN prevalence of at least 20%. Postoperative AKI incidence ranges from 12–36% in the literature. Assuming that at least 20% of our patients will be CAN-positive and that AKI incidence in CAN-positive patients will be at least 10% higher than in CAN-negative patients, with $\alpha = 0.05$ and $\beta = 0.2$, a minimum of 884 patients will be required.

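### Intraoperative transfusion is triggered by hematocrit and transfusion is compared between CAN groups, but no preoperative hemoglobin or hematocrit is recorded, so an imbalance at baseline, if there is one, could be neither seen nor adjusted for

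*Combined protocol and SAP*

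**What the plan says.** - **Trigger.** Section 4, Intraoperative Management: "Transfusion if Hct <27" (percent). No trigger is stated for the postoperative period.
- **Outcome.** Section 6 lists "Transfusion requirement" with no definition or time window. Section 2 places "Transfusion volume, IABP use, drainage volume" among the postoperative data. Section 1 states the aim these outcomes serve: "The impact of CAN on outcome parameters (mortality and morbidity").
- **Preoperative data.** Section 2 lists "Demographics and comorbidities (hypertension, diabetes, COPD, recent MI, atrial fibrillation, dyslipidemia"), then "Kidney function (BUN, creatinine, GFR"), then hemodynamics and baseline rSO₂. Hemoglobin, hematocrit and anemia are not listed, and anemia is not an exclusion in section 7.
- **Nearest other source.** The intraoperative list has "Hemodynamics, urine output, blood gases", without components or sampling times.
- **Analysis.** "Between-group comparisons for categorical variables will be performed using the chi-square test". Continuous variables are compared by t-test or Mann-Whitney U test. Multiple regression is planned only for AKI and neurological complications, and no covariates are named. Transfusion has no adjusted analysis.

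**The concern.** Under a fixed threshold, whether a patient is transfused depends on where the hematocrit started as well as on how far it fell. Starting hematocrit is therefore a direct determinant of intraoperative transfusion. CAN status is observed, not assigned, and the sample size section derives its expected prevalence from diabetes and prior MI. The plan thus expects CAN to go with comorbidity, and nothing in the design makes starting hematocrit equal in the two groups.

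If CAN-positive patients start lower, they will cross the trigger more often even when CAN has no effect, and the crude test will attribute the difference to CAN. If the groups are in fact balanced, the trial could not show it, so a true finding would be open to the same doubt. The value is also unavailable as a covariate for the primary outcome, AKI, where starting anemia is a plausible common factor. Recording diabetes and MI does not recover the hematocrit itself.

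**Working it through.** **1. The plan's own figure.** The point does not depend on the sample size, but the calculation below uses its group sizes. Take 20% CAN-positive (ratio 1:4), two-sided α = 0.05, power 80% and AKI of 30% v 20%. The 20% reference rate is back-solved, since the plan gives only a range of 12–36%. The pooled rate is (0.30 + 4×0.20)/5 = 0.22, and

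n₁ = [1.96·√(0.22×0.78×1.25) + 0.842·√(0.30×0.70 + 0.20×0.80/4)]² / 0.10² = 176.5, rounded up to 177.

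The total is 5×177 = 885, against 884 stated. Of 884 patients, 20% is 176.8, so 177 v 707 is used. The power function in step 3 returns 80.1% for 30% v 20% at these sizes.

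**2. Probability of crossing the trigger.** All hematocrit inputs are assumptions: starting value 40 (SD 4.5) in CAN-negative patients; a fall of 10 (SD 3) independent of the start; CAN-positive patients start d points lower; no CAN effect on the fall. The lowest value then has SD √(4.5² + 3²) = 5.41, and

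P(below 27) = Φ[(27 − (40 − d − 10))/5.41] = Φ[(d − 3)/5.41].

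**3. How often the crude chi-square test is significant.** With p₁ and p₀ from step 2 and pooled rate p̄:

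s₀ = √[p̄(1−p̄)(1/177 + 1/707)] and s₁ = √[p₁(1−p₁)/177 + p₀(1−p₀)/707].

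The probability is Φ[(p₁ − p₀ − 1.96·s₀)/s₁] plus the small opposite tail. For d = 1: p₁ = Φ(−0.370) = 0.356, p₀ = Φ(−0.555) = 0.290, p̄ = 0.303, s₀ = 0.0386, s₁ = 0.0398. This gives Φ[(0.0662 − 0.0757)/0.0398] = Φ(−0.24) = 0.41.

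| CAN-positive start lower by | Below 27, CAN+ v CAN− | Test significant |
|---|---|---|
| 0 | 29% v 29% | 5% |
| 0.5 | 32% v 29% | 14% |
| 1 | 36% v 29% | 41% |
| 1.5 | 39% v 29% | 73% |

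**4. Sensitivity, 1.5-point case.** A mean fall of 8 gives 67% and of 12 gives 75%. A starting SD of 3.5 (combined √(3.5² + 3²) = 4.61; 37% v 26%) gives 85%. A starting SD of 5.5 (combined √(5.5² + 3²) = 6.26; 41% v 32%) gives 61%. The size of the shift matters most.

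**5. Does adjustment remove it?** In simulated studies under the step 2 assumptions with d = 1.5, a logistic model with CAN alone flagged CAN in 72% of studies. With starting hematocrit added, it did so in 5%, the nominal level.

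**6. AKI, illustration only.** Suppose anemia is present in 30–50% of CAN-positive and 20% of CAN-negative patients, multiplies AKI risk by 1.5–2.0, and AKI risk without anemia is 12–20%. The spurious difference is (difference in anemia prevalence) × (base risk) × (risk ratio − 1). It runs from 0.10×0.12×0.5 = 0.6 points to 0.30×0.20×1.0 = 6 points, against the 10-point difference the trial is planned for. The anemia prevalences and the risk ratios are assumptions.

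**The case against.** **The imbalance is assumed.** A reader might infer that anemia does differ between the CAN groups, so that the transfusion result will be wrong. The documents do not support that. They link CAN to diabetes and MI, not to hematocrit, and at zero shift the error rate is the nominal 5%. This stands, and the point is therefore conditional.

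**The trigger and the outcome do not fully match.** The threshold is under intraoperative management, while volume is listed with the postoperative data beside drainage. If the outcome is meant to be postoperative transfusion, bleeding and unstated postoperative practice also determine it, and the table above does not describe it. It does not describe volume either. This stands as a limit on the figures. Section 6 sets no time limit, so intraoperative transfusion is not ruled out of the outcome, and the missing AKI covariate does not depend on this question.

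**Blood gases may contain a hematocrit.** They may, and an early sample might be close to baseline. But the plan specifies neither components nor timing, and section 4 starts crystalloid at induction. The samples cannot be relied on as a baseline, though the documents do not exclude them.

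**The value could be recovered later.** A reader might infer that omission from the data list makes adjustment permanently impossible. That goes too far, because a preoperative blood count is normally in the chart. What holds is that the dataset as planned will not contain it.

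**Transfusion is one of 13 items in section 6, and the lack of adjustment is broader than this variable.** Both are true and limit the weight of the point. Hematocrit still merits separate mention because the protocol's own rule makes it a determinant of the outcome.

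**Conclusion.** The point holds in conditional form. As written, the plan compares a threshold-driven outcome between non-randomized groups without recording the starting value of the variable that drives it. If CAN-positive patients start 0.5 to 1.5 hematocrit points lower, a crude test of crossing the intraoperative trigger would be significant in 14% to 73% of studies with no CAN effect, and in 5% if they start equal. These figures rest entirely on the stated assumptions and apply to intraoperative transfusion only. They show how sensitive the comparison is, and are not evidence that an imbalance exists in this population. The exposure of the AKI analysis is plausible, but the documents give no data from which to size it. The sample size is unaffected. This should be changed because the remedy is cheap; it does not invalidate the trial.

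**What to change.** 1. Add the last preoperative hemoglobin/hematocrit to the preoperative data list in section 2, copied from the existing blood count. For patients already enrolled, retrieve it from the chart.
2. Report it by CAN group, so that balance can be judged.
3. Compare transfusion requirement (logistic model) and transfusion volume between CAN groups with adjustment for it. Recording the value alone is not enough, since no adjusted transfusion analysis is planned. State the time window of the transfusion outcome, so that readers know whether the intraoperative trigger applies to it.
4. Name it as a preoperative covariate in the AKI regression.

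The cost is one extra data field and one extra model term, in models that routine software fits. The transfusion rule itself is not questioned.

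### Section 7 protects the CAN tests from drugs, lung disease and orthopedic problems but does not require sinus rhythm at testing, so in some patients rhythm may decide or tip the CAN group.

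*Combined protocol and SAP*

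**What the plan says.** Section 2 assigns CAN on the day before surgery "using Valsalva maneuver, sitting-to-standing test, and temperature sensitivity test". The rule is: "A positive result in at least two tests will confirm CAN". No measured variable, cut-off or rhythm condition is given for any test.

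Section 7 includes "All patients >18 years old scheduled for CABG requiring ECC". Three of its exclusions protect the tests: orthopedic problems that prevent standing, "Chronic respiratory diseases (bronchitis, asthma, COPD) affecting Valsalva reliability", and "Use of antiarrhythmic drugs affecting heart rate-based tests". AF, other non-sinus rhythm and pacing are not on the list.

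AF appears once in the document, among the preoperative comorbidities to be recorded in section 2 ("recent MI, atrial fibrillation, dyslipidemia"). Pacemakers are not mentioned at all.

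The Statistical Analysis section plans a multiple regression for AKI but names no covariates, and it plans no sensitivity analysis by rhythm.

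**The concern.** The exclusion list follows a clear principle: leave out patients in whom a CAN test cannot be read. It applies this to drugs that disturb heart rate-based tests but not to a rhythm that disturbs them. In AF the beat-to-beat intervals are irregular whatever the autonomic function. In a paced rhythm the rate response belongs to the device, although that is a secondary point because the documents are silent on pacing.

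The document refers to heart rate-based tests in the plural without naming them. If both the Valsalva and the sitting-to-standing tests are of this kind, rhythm alone could meet or defeat the two-of-three rule. If only one is, rhythm could still tip a patient who has one other positive result.

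Two results are exposed. The frequency of CAN, a stated objective, would be biased. The CAN–AKI difference would be diluted or, if AF carries its own AKI risk, partly manufactured.

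**Working it through.** **The plan's own figure.** From the Sample Size Calculation: 20% CAN-positive (1:4), a 10-point AKI difference, α = 0.05, β = 0.2. The CAN-negative AKI rate is not stated (the text gives a 12–36% range), nor is sidedness. Taking 20% v 30%, two-sided, with pooled rate (0.30 + 4 × 0.20)/5 = 0.22:

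n₁ = [1.96·√(0.22 × 0.78 × 1.25) + 0.8416·√(0.30 × 0.70 + 0.20 × 0.80/4)]² / 0.10² = (0.9077 + 0.4208)²/0.01 = 176.5

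This rounds to 177 CAN-positive and 707 CAN-negative, total 884, which matches the plan. Power at 177 v 707 is 80.1%. The 20% rate is thus inferred from the match.

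**Misreading model.** Let f be the share tested while in AF, after the drug exclusion. The documents do not give f; I assume 3–10% and also show 1–2%. AF is taken as independent of true CAN, so these patients have the average AKI risk of 0.2 × 30% + 0.8 × 20% = 22%.

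Power = Φ[(d − 1.96·s₀)/s₁], with s₀ = √[p̄(1 − p̄)(1/n₁ + 1/n₂)] and s₁ = √[p₁(1 − p₁)/n₁ + p₂(1 − p₂)/n₂].

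*All read CAN-positive.* Apparent prevalence P = f + 0.2(1 − f). Observed risk in the positive group = [0.2(1 − f) × 0.30 + f × 0.22]/P; in the negative group it stays 0.20. At f = 10%: P = 0.28, risk = (0.054 + 0.022)/0.28 = 0.2714, d = 0.0714, n₁ = 247.5, n₂ = 636.5, s₀ = 0.0310, s₁ = 0.0324, power 63%.

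*All read CAN-negative.* Apparent prevalence Q = 0.2(1 − f). Risk in the positive group stays 0.30; in the negative group it is [0.8(1 − f) × 0.20 + f × 0.22]/(1 − Q). At f = 10%: Q = 0.18, risk = (0.144 + 0.022)/0.82 = 0.2024, d = 0.0976, power 75%.

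*Excluded without replacement.* N = 884(1 − f), 30% v 20%.

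| f | All positive: apparent CAN, d, power | All negative: apparent CAN, d, power | Excluded: power |
|---|---|---|---|
| 1% | 20.8%, 9.6, 78% | 19.8%, 10.0, 80% | 80% |
| 2% | 21.6%, 9.3, 77% | 19.6%, 9.9, 79% | 79% |
| 3% | 22.4%, 8.9, 75% | 19.4%, 9.9, 79% | 79% |
| 5% | 24.0%, 8.3, 71% | 19.0%, 9.9, 78% | 78% |
| 10% | 28.0%, 7.1, 63% | 18.0%, 9.8, 75% | 76% |

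**Spurious difference.** Suppose CAN has no effect (22% AKI in both groups), AF adds e points of AKI, and all AF patients read positive. The observed difference is f·e/P. At f = 3%, e = 10: 0.03 × 10/0.224 = 1.3 points. At f = 10%, e = 20: 0.10 × 20/0.28 = 7.1 points. The chance of a significant result is 7% and 60% respectively, against 5% nominal. The excess e is also an assumption.

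**Adjustment for AF.** In the all-positive case at f = 10%, the crude odds ratio is (0.2714/0.7286)/(0.20/0.80) = 1.49. With an AF term, the CAN coefficient depends only on non-AF patients and returns to (0.30/0.70)/(0.20/0.80) = 1.71. In the no-effect case with e = 20, the crude (0.2914/0.7086)/(0.22/0.78) = 1.46 returns to 1.00. The apparent CAN frequency stays at 28% instead of 20%.

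**The case against.** **The drug exclusion may already remove most AF patients.** It removes some. It does not reach untreated AF, drugs that a site does not count as antiarrhythmic, or pacing. How many remain is unknown. If it is 1–2%, the loss of power is small even when every one is misread.

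**The largest figures need every AF patient to be read positive.** This stands. The documents do not say which tests use heart rate, what is measured or where the cut-offs lie, so the direction cannot be settled. If all read negative, power is 79–75%, and excluding these patients without replacement gains at most about one point. A reader might infer that arrhythmia generally decides the group; the two-of-three rule and the missing definitions do not support more than that it can decide or tip it.

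**Recording AF might be taken to show that such patients are expected.** It does not. COPD is in the same recorded list ("Demographics and comorbidities (hypertension, diabetes, COPD, recent MI, atrial fibrillation, dyslipidemia") and is excluded in section 7. Eligibility follows only from the broad inclusion criterion together with the absence of AF from the exclusions.

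**AF is recorded and a regression is planned, so the analysis can deal with it.** A reader might infer that adjustment cannot help, but in the modelled all-positive case it removes the bias in the CAN–AKI estimate. What remains is that no AF term is prespecified, a history of AF is not the rhythm at testing, and the CAN frequency stays biased.

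**Conclusion.** The gap is real: the plan has no rhythm condition for tests that it describes as heart rate-based and that define the exposure. Its size is uncertain. With an assumed 3–10% tested in AF and the inferred 30% v 20% AKI rates, power is 75–63% if all read positive and 79–75% if all read negative, against 80% planned. These are limiting cases of complete misreading. The spurious difference of 1.3–7.1 points further assumes 10–20 points of excess AKI in AF and all-positive reading.

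The documents do not support calling 884 wrong on this account, since it reproduces on its own assumptions. Nor do they support citing 63% as the expected power. The change is worth making because it is cheap and completes the plan's own set of test-validity exclusions. Confidence is medium.

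**What to change.** Add an exclusion to section 7: *Not in sinus rhythm (atrial fibrillation or flutter, paced rhythm) at the time of the CAN tests.* Record the rhythm at testing on the case report form, keep patients with paroxysmal AF who are in sinus rhythm when tested, and report the number excluded.

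If the sponsor prefers to keep these patients for the CAN-frequency objective, prespecify that the primary CAN–AKI comparison uses patients tested in sinus rhythm, and report the others separately.

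The cost is one line, one tick-box and a few percent of candidates. To keep 884 analysed, 884/(1 − f) must be considered: 884/0.97 = 912 at 3%, 884/0.95 = 931 at 5%, 884/0.90 = 983 at 10%. The result would not generalise to patients in AF.

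### Student's t-test is specified with no provision for unequal variances although unequal groups are expected, so secondary continuous comparisons can miss the 5% level if the CAN groups differ in spread

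*Combined protocol and SAP*

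**What the plan says.** The Statistical Analysis section has two routes for continuous variables. The choice depends on skewness and kurtosis: "Variables with distribution between -1.5 and +1.5 will be considered normally distributed (parametric), otherwise non-parametric". On the parametric route, "Between-group comparisons will be performed using the independent Student's t-test, and within-group temporal comparisons using the paired Student's t-test". On the other route, "Between-group comparisons for non-parametric variables will be performed using the Mann-Whitney U test". No variance check and no unequal-variance form of the t-test is mentioned, and the text does not say whether the screen is applied to the combined sample or within each group.

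The Sample Size Calculation section gives the expected balance of the groups, "Assuming that at least 20% of our patients will be CAN-positive", and the total, "with $\alpha = 0.05$ and $\beta = 0.2$, a minimum of 884 patients will be required". No SD or variance is given for any continuous variable.

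**The concern.** Student's t-test, in its usual meaning, estimates one common variance from both groups. When the groups differ in size, that estimate is dominated by the larger group. If the smaller group is the more variable, the standard error is too small and false positives exceed 5%. If the smaller group is the less variable, the standard error is too large and the test loses power. The robustness of t-tests to non-normality in large samples does not help here, because the bias depends on the ratio of group sizes and the ratio of SDs, not on the total number of patients.

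The comparisons at stake are CAN-positive against CAN-negative means for continuous variables that pass the screen. Regional cerebral oxygen saturation is the most prominent, since its relationship with CAN is one of the aims listed in Section 1. Renal values and hemodynamics are other examples.

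**Working it through.** **Inputs from the documents.** Total 884; CAN prevalence at least 20%; alpha 0.05 and power 80%; an AKI difference described as "AKI incidence in CAN-positive patients will be at least 10% higher than in CAN-negative patients"; and a background rate, "Postoperative AKI incidence ranges from 12–36% in the literature".

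**Assumptions.** Two-sided testing (sidedness is not stated). The 10% is read as 10 percentage points. AKI in CAN-negative patients is 20%, which lies within the stated 12–36%. Student's t-test means the pooled-variance form. The ratio r = SD(CAN-positive)/SD(CAN-negative) is varied, because the documents give nothing to fix it.

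**Step 1: reproduce 884.** For two proportions of 30% and 20% with a 1:4 ratio and no continuity correction, the mean proportion is (0.30 + 4 × 0.20)/5 = 0.22, and

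n₁ = [1.96·√(1.25 × 0.22 × 0.78) + 0.8416·√(0.30 × 0.70 + 0.20 × 0.80/4)]² / 0.10² = (0.9077 + 0.4208)² / 0.01 = 176.5, rounded up to 177.

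n₂ = 4 × 176.505 = 706.02, rounded up to 707. The total is 177 + 707 = 884. The plan's figure is therefore consistent with 20% prevalence taken as a 1:4 ratio.

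**Step 2: type I error of the pooled test.** Set the CAN-negative SD to 1.

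- True variance of the difference in means: V_true = r²/177 + 1/707.
- Variance that the pooled test uses: V_pool = [(176r² + 706)/882] × (1/177 + 1/707).
- Large-sample size: 2 × [1 − Φ(1.96/√(V_true/V_pool))].

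Worked case, r = 1.5: V_true = 2.25/177 + 1/707 = 0.01413. The pooled variance is (176 × 2.25 + 706)/882 = 1.2494, so V_pool = 1.2494 × 0.007064 = 0.00883. √(V_true/V_pool) = 1.265, and 1.96/1.265 = 1.549. The size is 12.1%.

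| r | √(V_true/V_pool) | Type I error |
|---|---|---|
| 0.67 | 0.793 | 1.3% |
| 0.8 | 0.876 | 2.5% |
| 1.0 | 1.000 | 5.0% |
| 1.1 | 1.059 | 6.4% |
| 1.2 | 1.115 | 7.9% |
| 1.5 | 1.265 | 12.1% |
| 2.0 | 1.458 | 17.9% |

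Simulation of normal data, 40,000 runs per ratio, agrees for Student's test: 1.3%, 8.1%, 12.3% and 18.1% at r = 0.67, 1.2, 1.5 and 2. Welch's test stayed at 4.9% to 5.2% across r = 0.67 to 2. Ten times the patients at the same balance (1770 against 7070) leaves the formula's results at 7.9%, 12.1% and 17.9% for r = 1.2, 1.5 and 2.

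**Step 3: vary the prevalence.** With the total held at 884:

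| CAN prevalence | Groups | r = 1.2 | r = 1.5 | r = 2 |
|---|---|---|---|---|
| 20% | 177 / 707 | 7.9% | 12.1% | 17.9% |
| 30% | 265 / 619 | 6.8% | 9.3% | 12.5% |
| 40% | 354 / 530 | 5.9% | 7.0% | 8.2% |

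**Step 4: does the shape screen intervene?** For normal data, with the screen applied to the combined sample and kurtosis taken as excess, it passes 100% of variables at r = 1.25, 99.5% at 1.5, 88% at 1.75 and 44% at 2. It therefore does not catch moderate differences in spread. Near r = 2 more than half the variables go to Mann-Whitney instead, whose simulated error (2,000 runs) is 8.3% at r = 1.5 and 11.1% at r = 2.

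**Step 5: the opposite direction.** At r = 0.67 the pooled test's effective critical value is 1.96/0.793 = 2.47. An effect that Welch's test detects with 80% power lies 1.96 + 0.84 = 2.80 standard errors from zero, so Student's power is about Φ(2.80 − 2.47) = Φ(0.33) = 63%. Simulation gave 62%.

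**The case against.** The strongest objection is that nothing in the documents suggests the two groups differ in spread. No SD is reported for any variable, and with equal SDs the planned test is correct. That stands. A reader might infer that every comparison on the parametric route has the wrong error rate, or that the plan carries an 8–18% false-positive rate. The documents support neither: those figures belong to assumed SD ratios of about 1.2 to 2, and the test is conservative if CAN-positive patients vary less.

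The 1:4 balance is also not a design feature. It follows from an anticipated minimum prevalence in an observational cohort, so reading it as a planned split goes too far. Step 3 shows the inflation shrinking as prevalence rises towards one half.

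The screening limits might be blamed too. They are not the cause: the distortion comes from pooling variances in unequal groups. At large SD ratios a combined-sample screen would divert many variables from the t-test, so 17.9% describes variables actually tested by Student's t, not the whole procedure. Nor are the limits ambiguous between raw and excess kurtosis, since a lower limit of −1.5 makes sense only for excess kurtosis.

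Finally, AKI incidence is binary and goes to chi-square and regression, and most outcomes in Section 6 are categorical. Durations and drainage may well be skewed enough to leave the t-test route. This limits the scope of the point but does not remove it.

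**Conclusion.** The point holds as a conditional weakness in the secondary analyses. The plan names a test that is sensitive to unequal variances, expects unequal groups, and provides no safeguard. The size depends on an SD ratio that must be assumed. At the minimum prevalence, modest ratios of 1.1 to 1.2 give 6.4% to 7.9%, and a ratio of 2 gives 17.9% for variables that stay on the t-test route. The reverse direction costs power. All of this takes Student's t-test to mean the pooled form, which is conventional but not stated; if Welch's form was intended, the text still needs to say so.

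A reader might infer that the primary result or the sample size is at risk. It is not, because both rest on a comparison of proportions. This is a cheap improvement to the continuous secondary and descriptive comparisons.

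**What to change.** In the Statistical Analysis section, replace the independent Student's t-test with Welch's (unequal-variance) t-test for between-group comparisons of variables classed as parametric. The paired test for within-group changes can stay as it is.

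The cost is one line of wording and a negligible loss of power when variances are equal: in simulation, 79.9% for Welch against 80.1% for Student. The change does not alter the Mann-Whitney route, which has its own sensitivity to unequal spread (Step 4).

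### Does taking the 20% CAN prevalence from HRV-based studies, rather than from the study's own two-of-three test rule, undermine the sample size of 884?

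*Combined protocol and SAP*

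**What the plan says.** The Sample Size Calculation reaches its prevalence in three steps. It starts from an outside rate: "Based on previous studies using heart rate variability (HRV) for CAN diagnosis, the prevalence of CAN after myocardial infarction (MI) is approximately 60" percent. It then gives the share of patients at risk: "In the CABG population, approximately 30% of patients have diabetes and/or MI". It concludes: "Therefore, we anticipate a CAN prevalence of at least 20" percent. With that prevalence, AKI at least 10% higher in CAN-positive patients, α = 0.05 and β = 0.2, it states that "a minimum of 884 patients will be required". For AKI it cites a literature range of 12–36% and does not name the two rates used.

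Section 2 (Materials and Methods) classifies patients differently: "Preoperative CAN diagnosis will be performed 1 day before surgery using Valsalva maneuver, sitting-to-standing test, and temperature sensitivity test". The rule is: "A positive result in at least two tests will confirm CAN". Section 7 excludes patients for "Use of antiarrhythmic drugs affecting heart rate-based tests", so at least some of the three tests rely on heart rate, as HRV does. Section 1 lists among the questions to be studied: "The incidence of CAN in patients scheduled for isolated CABG".

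The documents give no minimum number of CAN-positive patients and no check of prevalence during enrolment.

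**The concern.** Patients are not allocated to CAN groups. The split is whatever the tests find, and the smaller group limits the precision of the primary comparison. The plan takes its expected split from a different diagnostic method, mostly in post-MI patients, and lists the frequency of CAN as something still to be learned. If the two-of-three rule is stricter than HRV, 884 patients could contain well under 177 CAN-positive patients, and a real 10-point difference in AKI could be missed. CAN status is known the day before surgery, so a shortfall could be seen during enrolment without AKI data. On that reasoning, a prevalence check looks like a cheap safeguard that was left out.

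**Working it through.** **Inputs from the Sample Size Calculation.** α = 0.05; power 0.80 (β = 0.2); 20% CAN-positive, a 1:4 ratio; difference 10%; total 884.

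**Assumptions, because the plan is silent.** Absolute difference, two-sided test, chi-square without continuity correction, AKI 20% in CAN-negative and 30% in CAN-positive patients. The 20% is back-solved as the value that returns 884. A relative reading of 10% would need at least 8,855 patients over the cited AKI range, so the absolute reading is clearly the intended one.

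**1. Reproducing 884.** With p₁ = 0.30, p₂ = 0.20, k = 4 and p̄ = (0.30 + 4 × 0.20)/5 = 0.22:

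n₁ = [1.960·√(p̄(1−p̄)(1+1/k)) + 0.842·√(p₁(1−p₁) + p₂(1−p₂)/k)]² / 0.10²

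= [1.960·√(0.1716 × 1.25) + 0.842·√(0.21 + 0.04)]² / 0.01

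= (0.9077 + 0.4208)² / 0.01 = 176.5, rounded up to 177.

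n₂ = 4 × 176.5 = 706.02, rounded up to 707. The total is 884, as stated.

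**2. The prevalence that the plan's own figures give.** 0.60 × 0.30 = 0.18. This applies the post-MI rate to everyone with diabetes and/or MI and counts no CAN elsewhere. Reaching 0.20 takes a further 0.02 from the other 70% of patients: 0.02/0.70 = 2.9%.

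**3. Power at 884 by prevalence.** Power = Φ{[0.10 − 1.960·√(p̄(1−p̄)(1/n₁+1/n₂))] / √(0.21/n₁ + 0.16/n₂)}. At 18%, n₁ = 159, n₂ = 725 and p̄ = 0.218: (0.10 − 1.960 × 0.03616)/0.03926 = 0.742, and Φ(0.742) = 0.771.

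| CAN-positive | Patients | Power, AKI 30% vs 20% | Power as CAN-negative AKI runs from 12% to 36% |
|---|---|---|---|
| 25% | 221 | 85% | not needed here |
| 20% (plan) | 177 | 80% | 90% to 69% |
| 18% (60% × 30%) | 159 | 77% | 88% to 65% |
| 15% (illustrative) | 133 | 72% | 84% to 59% |
| 10% (illustrative) | 88 | 58% | 72% to 46% |

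Other formulas calibrated to about 884 (continuity-corrected, unpooled, one-sided) give 70–72% at 15% and 54–60% at 10%, so the pattern does not depend on the formula.

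**4. What a mid-enrolment check would do.** Suppose CAN status is counted at 442 patients and enrolment is raised if fewer than 20% are positive. At a true prevalence of exactly 20%, the rule fires when 88 or fewer are positive (442 × 0.20 = 88.4), a binomial probability of 0.51. By simulation, the mean total is 911 at a true 20%, 1,112 at 15% (228 more than 884) and 1,574 at 10% (690 more). Type I error stays near 0.05. The rule restores 80% power only if CAN-negative AKI is in fact 20%. At 20% CAN-positive, the AKI rate alone moves power from 90% to 69%, a wider span than the 8 points lost between 20% and 15% CAN-positive.

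**The case for a change.** The strongest case for a change is that the decisive input has no support under the study's own rule, that the plan's figures multiply to 18% and not 20%, and that a shortfall can be corrected only while enrolment is open. One count of data already collected would reveal it.

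Part of this stands. The diagnostic methods do differ, no prevalence is given for the two-of-three rule, the AKI rates and the sidedness are unstated, and the plan does not say what happens if CAN-positive patients are few.

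The rest is weaker than it looks. A different method does not mean a lower rate: prevalence under the rule could lie on either side of 20%, and at 25% power would be 85%. The 18% product counts no CAN in patients without diabetes or MI, and a rate of about 3% there closes the gap. It is also wrong to assume that enrolment closes at 884. The plan calls that figure a minimum and includes all patients scheduled for CABG with ECC, so it leaves room to continue. Finally, the check is cheap to run but not to obey: it commits the sponsor to more patients in about half of studies that are exactly on target, and to several hundred more if prevalence is low.

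**Conclusion.** No change is called for. The figure 884 is correct under the conditions attached to it, and the plan already makes it conditional on at least 20% being CAN-positive. The only shortfall that its own figures support is 18%, worth about 3 points of power (77% against 80%). The 72% and 58% figures are sound arithmetic at prevalences that the documents do not give. All of these assume AKI of 30% versus 20% and a two-sided test.

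Relabelling 20% as a planning assumption, or writing out the AKI rates and sidedness, would put on paper what a reader can already reconstruct and would alter neither the design nor the analysis. A prevalence-triggered extension is a legitimate option, but it is a trade-off: it buys protection against one uncertain input with potentially hundreds of patients and leaves the AKI rate unmonitored. For an observational cohort with a stated minimum, leaving it out is a fair choice. The observed CAN split will be known at analysis, because its frequency is a study objective, and the confidence interval for the AKI difference will show whatever precision was achieved.
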